4. For samples determined stable according to defined criteria STA® - Liatest® D-Di XL result, combined with the result of the Wells Score assessment at the first visit, will be used for comparison to reference (imaging or follow-up) and computation of accuracy parameters (sensitivity, NPV, specificity and PPV).

It is important to note that VIDAS assay is used to test stability of frozen plasma samples with respect to D-dimer, *and is not meant to substitute for STA® - Liatest® D-Di XL*. In this context, our interest is in stability as a *characteristic of the sample* (not the device) and is best assessed by VIDAS assay, which is known to provide the greatest precision of cleared products and in this sense can be considered a “reference standard” for sample stability. Only after stability is established it is appropriate to evaluate D-dimer with the test device STA® - Liatest® D-Di XL.

Patients with DVT and PE will be analyzed as separate groups. Therefore, enrolment in each group will be monitored separately and will be stopped when the desired target per indication is reached.

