6.2 VTE DIAGNOSIS AND STUDY PROCEDURES

At all sites, VTE diagnosis will follow SOC procedures for diagnosis and treatment.

For patients suspected of VTE, this may include imaging only, or D-Dimer test followed by imaging or PTP score + D-Dimer testing + imaging. For all patients for whom VTE is not confirmed by imaging at the initial visit, the study will require that a 3-month follow-up is performed.

- Irrespective of the procedures used locally for VTE diagnosis, sites will be asked to evaluate patients with symptoms consistent with VTE (DVT and/or PE) using the Wells score without knowledge of D-Dimer and/or imaging results. The Wells score result may or may not be used for VTE diagnosis depending on sites' SOC.
- About 12 ml of venous blood will be taken from unlikely subjects (see definition on page 10) in order to obtain at least 6 aliquots of 1 mL of patient plasma each: plasma aliquots will then be banked frozen at -70°C
- STA® - Liatest® D-Di XL will later be used on banked frozen samples to assess assay's accuracy relative to the reference standard (imaging or 3-month follow-up). Only samples determined stable using the procedure described in Section 4.2 will be included in the study.
- Samples may also be used in future studies to evaluate new D-dimer test products to be used as improved diagnostic tools for DVT and/or PE (currently under development by Stago).

Plasma from patients with high Wells score will not be collected in the study.

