6.7 FOLLOW UP

Patients for whom VTE was excluded as per SOC will be followed for 3 months to evaluate potential development of DVT and/or PE.

This follow-up will be performed by the clinician, the study coordinator or the nurse to obtain information regarding development of DVT and/or PE in the 3 months (i.e. 90 days) following Visit 1. The follow-up will have an allowed window of 1 month. Therefore it will take place in the period between 3 and 4 months (i.e. 90 to 120 days) after patient's first visit. The follow-up may be done using several methods according to site choice:

- Phone call to the patient,
- Medical record review if at enrollment patient states he/she does all its medical consultation at the investigation site and if he/she agrees that follow-up will be done by review of its medical record,
- Email to the patient asking the patient to call one site study representative if patient has given its consent to be contacted via email and server for email is secure,
- Call to family doctor in case patient is not answering the call.

The three-months follow-up information may be recorded directly in the CRF, in this case the CRF is considered as Source Document.

In addition, for female patients pregnant at the time of the follow up contact, all efforts will be done to determine if patient had an undetected pregnancy at visit 1, in which case the patient will be excluded from the study due to violation of an exclusion criterion.

If a patient cannot be contacted to collect follow-up information even beyond the 120 days from visit 1, he/she will be considered "lost to follow-up". But before declaring that a patient is "lost to follow-up", the PI (or his/her team) must do his/her best effort to contact patients and attempts should be made via all available routes, and when necessary, patients should be traced through relatives and examination of State death records. A certified letter should be sent to the permanent address on file. The methods used to attempt to contact the patient should be noted.

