9.2 DESIGN CONSIDERATIONS

This is a prospective, multi-center study which will recruit consecutive subjects suspected of VTE. The population of interest includes those subjects classified “unlikely” by the Wells score system as specified in the CLSI guideline.

Following are central elements of this trial's design:

Separate Statistical Testing of DVT and PE: Logistically this trial will be conducted as a single study. However data obtained will be analyzed separately for DVT and PE subjects. Trial design is identical for both indications and statistical analyses are almost identical.

Blinding of follow-up data: All "unlikely" subjects excluded at Visit 1 by SOC D-dimer negative or by negative imaging will be followed for occurrence of VTE for up to three months. To minimize possible bias during follow-up:

- Testing of STA® - Liatest® D-Di XL will be performed by testing site staff blinded to imaging or follow up results. A procedure will be set up before testing starts to ensure that blinding is rigorously maintained at testing sites
- Stago will be exposed to recruitment rates and count of reference-positive cases for the purpose of blind sample size re-estimation. Company will be blinded to all other data (including, of course, device outcome). A standard operating procedure (SOP) will be developed to ensure that this in fact is the case.
- Company and designated statisticians will be blind to efficacy data throughout the trial. The electronic data capture (EDC) provider will create a file accessible to data management and statistics that includes all study data excluding Device result (level of D-dimer) and Device diagnosis (positive or negative). This will enable counting reference-positive cases blind to outcome, which is needed for blind sample size re-estimation. The provider will create a separate file that is accessible to the provider only, in which subjects' D-dimer results are entered. Files will be merged at data lock, after the final SAPs have been completed and signed. The procedure will be drawn up in an SOP.

STA® - Liatest® D-Di XL testing for the purpose of this trial will be done on banked samples collected from subjects at Visit 1.

Special efforts will be made by PI (or his/her team) to obtain follow-up clinical outcome for subjects who could not initially be reached by the standard follow-up procedures. Such efforts may include attempts to trace subjects through relatives and examination of State death records.

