9.3 ENDPOINTS

Primary Efficacy

For each "unlikely" subject, VTE diagnosed dichotomously (positive/negative) by:

- Reference Standard, which includes data obtained by imaging or follow-up,
- Device

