9.4 ANALYSIS SETS

The Primary efficacy analysis set will consist of all "unlikely" VTE subjects for whom there are valid observed values on both STA® - Liatest D-Di XL and Reference Standard (imaging or follow up). This includes "unlikely" subjects suspected of PE, or DVT or both; the latter will be included in both of the separate PE and DVT analysis sets. "Unlikely" D-dimer negative subjects having imaging result at Visit 1 will have imaging as reference. Device result is considered valid if it is not missing, its associated QC results are in the QC ranges and is deemed stable after thawing according to criteria provided in Section 4.2. Subjects with major protocol deviations likely to affect outcome will be excluded by blind review³. In line with CLSI guidelines, distal DVT subjects are not included in the primary efficacy analysis set for the DVT indication.

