- Sites within US and OUS separately (enrolling sites with at least 20 subjects will be included separately. Sites with a smaller number of subjects will be combined into a single, "other" site). This is a test of site poolability within US and OUS separately.
- Region (US, OUS), which is a test of poolability of the US and OUS populations,
- PTP (measured by validated and standardized test).

Effect of covariates will be assessed for each covariate individually using the following logistic regression model:

Device = Cov + Reference Standard + Cov*Reference Standard

Where,

Device – D-dimer XL result (dichotomous)

Reference Standard – Diagnosis by imaging or follow-up (dichotomous)

Cov – Relevant covariate (categorical or continuous, depending on covariate)

Additional potential covariates will be compared between US and OUS and, if found significant, will be analyzed using the model described above.

In this model we are interested in the Cov*Reference interaction, whereby a significant result indicates that Device performance relative to Reference Standard is affected by the covariate.

Secondary Analysis

The following will be provided for Primary analysis sets:

- Specificity,
- Positive Predictive Value,
- Positive and negative likelihood ratios.
- Prevalence of reference positive cases

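### Section 9.4 makes Visit 1 imaging the reference for imaged D-dimer-negative subjects and does not say how a VTE found in their required 3-month follow-up counts

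*Combined protocol and SAP*

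**What the plan says.** Section 9.3 defines the primary endpoint by the Device and the "Reference Standard, which includes data obtained by imaging or follow-up". Section 4.2 says the D-Di XL result "will be used for comparison to reference (imaging or follow-up) and computation of accuracy parameters", and the covariate model in 9.6 uses the same pair of sources. None of these gives an order of precedence or a rule for combining the two.

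Section 9.4 then adds, for 'unlikely' subjects, that "D-dimer negative subjects having imaging result at Visit 1 will have imaging as reference". It does not say which D-dimer this is. The study has three: the standard-of-care (SOC) assay, VIDAS, and D-Di XL (the Device).

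Follow-up is not limited to subjects without imaging. Section 6.2: "For all patients for whom VTE is not confirmed by imaging at the initial visit, the study will require that a 3-month follow-up" is done. Section 9.2 says that 'unlikely' "subjects excluded at Visit 1 by SOC D-dimer negative or by negative imaging will be followed for occurrence of VTE". Section 6.7 describes the aim as obtaining "information regarding development of DVT and/or PE in the 3 months (i.e. 90 days) following Visit 1".

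The local work-up varies. According to 6.2, "this may include imaging only, or D-Dimer test followed by imaging or PTP score + D-Dimer testing + imaging", so some imaged subjects may have no SOC D-dimer result.

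**The concern.** The study requires 3-month follow-up in subjects with negative imaging. For one subgroup of them, 9.4 read literally leaves the outcome of that follow-up out of the reference standard. A VTE diagnosed during follow-up would then be scored differently according to whether the subject had been imaged at Visit 1, although it is the same event. For imaged subjects with a positive SOC D-dimer, or none, the supplied text gives no rule at all.

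The reference standard determines both co-primary endpoints, and by the protocol's own account (9.2, 9.5) sensitivity drives the sample size. The sensitivity goal allows few false negatives, so moving a single subject between cells can matter. Section 9.2 also has reference-positives counted during the trial for blinded re-estimation, and DVT enrolment is still open. That count needs a defined rule too.

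**Working it through.** **Step 1: how the readings classify a VTE found in follow-up ('unlikely' subjects)**

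| Visit 1 status | 9.4 read literally | Either source positive (composite) |
|---|---|---|
| Not imaged | positive (follow-up is the only source) | positive |
| Imaging negative, D-dimer-negative | negative | positive |
| Imaging negative, D-dimer-positive | no rule stated | positive |
| Imaging negative, D-dimer not done | no rule stated | positive |

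**Step 2: direction.** Take the SOC meaning of D-dimer in 9.4. For the second row, the literal reading scores a Device-negative subject as a true negative instead of a false negative (FN), which raises sensitivity. It scores a Device-positive subject as a false positive instead of a true positive (TP), which lowers sensitivity. The net direction depends on Device results that nobody has seen.

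**Step 3: the plan's own figure.** Inputs from 9.5 and 9.6: 115 reference-positives, sensitivity 98%, goals of lower confidence limit (LCL) ≥ 0.90 and point estimate ≥ 0.95, exact two-sided 95% interval, power at least 90%. With x TP among n positives, LCL = 2.5th percentile of Beta(x, n − x + 1).

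- 110/115 = 0.9565, LCL 0.9015: pass. 109/115 = 0.9478, LCL 0.8899: fail. So at most 5 FN, and 110 is the minimum for both goals, as 9.5 states.
- Power = P(Bin(115, 0.02) ≤ 5) = 97.1%, consistent with 'at least 90%'.
- At the 121 PE positives reported in 9.5: 116/121, LCL 0.9062, pass; 115/121, LCL 0.8952, fail.
- Maximum FN that passes: 4 at 113 positives, 5 at 114 to 126, 6 at 127.

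**Step 4: adding late VTEs to the reference.** Let k be the number of Device-negative late VTEs that the composite rule counts as FN and the literal reading counts as true negatives. The documents give no k, so the range below is an assumption.

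- From 5 reported FN, k = 1 reverses a pass: 110/116, LCL 0.8908; 116/122, LCL 0.8960.
- From 2 reported FN (0.02 × 115 = 2.3 expected), k = 4 is needed: 113/119, LCL 0.8935; 119/125, LCL 0.8985.
- The chance of exactly 5 FN at 98% sensitivity is 5.3% at 115 positives and 6.1% at 121.

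For k up to 3 the total stays between 114 and 126, so power = P(Bin(n, 0.02) ≤ 5 − k):

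| k | n = 115 | n = 121 |
|---|---|---|
| 0 | 97.1% | 96.5% |
| 1 | 91.8% | 90.4% |
| 2 | 80.1% | 77.6% |
| 3 | 59.5% | 56.3% |

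Under the literal reading power stays at the k = 0 row. For scale, 3,054 − 121 = 2,933 PE subjects were not counted positive. One case is 1/2,933 = 0.03% of them and two are 0.07%.

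Late VTEs that are Device-positive work the other way, but slowly. From 5 reported FN, one added FN is offset only if 11 TP (at 115) or 5 TP (at 121) are added as well. Both give 121/127, LCL 0.900005.

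**Step 5: NPV.** The planning values imply 2.3/0.004 = 575 Device negatives. With 17 FN, 558/575 = 0.9704 with LCL 0.9531, which passes. The first failure is at 18 FN (557/575 = 0.9687, below the 0.97 point goal). A few late VTEs do not threaten NPV.

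**The case against.** A reader might infer more than the text supports.

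- *9.4 contradicts 9.3.* Only if 'imaging or follow-up' means positive by either source, and 9.3 does not say that. It can equally name two alternative sources, with 9.4 stating which applies to one subgroup. The better-supported tension is with 6.2, 6.7 and 9.2, which require follow-up after negative imaging without saying how it enters the reference.
- *The index test selects its own reference.* The context points to the SOC assay. Section 9.2 writes 'SOC D-dimer negative' for Visit 1, reference-positives are counted from a file without the Device result, and 9.4 itself uses 'Device result' as a separate term. What stands is that 9.4 does not say so.
- *The rule favours the Device.* Step 2 shows that it can act in either direction.

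The other side has further points. The sentence sits under Analysis Sets and may be meant only as an evaluability rule: imaging suffices when follow-up is missing. That is plausible, but the wording assigns a reference and does not merely admit a subject. The separate PE and DVT SAPs (9.1) and the design diagrams are not in the supplied text and may settle the matter. Section 2.1 says that imaging need not be performed after a negative D-dimer in these patients, so the subgroup may be small. With one hidden FN, power is still 91.8% or 90.4%. Finally, 6.7 speaks of development of VTE, so some late events may be new and not missed at Visit 1. These points limit the size of the concern. They do not supply the missing rule.

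**Conclusion.** The concern holds as a gap in the definition of the primary reference, at the low end of what should be fixed and with moderate confidence. Section 9.4 read literally ignores follow-up for imaged D-dimer-negative subjects, the D-dimer is not named, and no supplied passage covers imaged subjects who were D-dimer-positive or not tested. The text does not establish a contradiction with 9.3, a circular reference or a bias towards success.

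The number of affected subjects and the net direction are unknown. The expected effect is small if few cases occur and true sensitivity is near 98%, and the effect on NPV is negligible. The point matters because the margin is 5 FN at any count from 114 to 126 positives, so one reclassified subject can settle a borderline result.

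The documents do not say whether the 121 PE positives already include VTEs found after negative imaging. If they do, the literal reading would remove those found in D-dimer-negative subjects. The 5-FN limit would still hold down to 114 positives.

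**What to change.** Before the Device file is merged, replace the 9.4 sentence with one rule that depends on no D-dimer result, and use it in both SAPs and in the blinded count of DVT positives:

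- Reference-positive: Visit 1 imaging is positive, or a VTE is diagnosed in the 3-month follow-up.
- Reference-negative: neither of these, with negative Visit 1 imaging or completed follow-up. Imaging-negative subjects without follow-up stay evaluable.

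Leave the handling of PE versus DVT events and of distal DVT as the protocol and SAPs define it, but state it explicitly for subjects who are positive only for the other indication. An example is a PE-suspected subject with positive leg imaging and no chest imaging. Add one sensitivity analysis that uses Visit 1 imaging alone for imaged subjects. If the SAPs already contain such a rule, align 9.4 with them.

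The cost is a short text change in 9.4 and the SAPs plus one extra analysis, with no new data collection. The timing matters: 9.2 merges the files at data lock after the SAPs are signed, and PE data cleaning is under way. After the merge the rule could no longer be chosen without knowledge of Device results. The downside is that some late VTEs may be new events, so estimated sensitivity may be slightly less favourable. The sensitivity analysis shows by how much.

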9.5 SAMPLE SIZE CONSIDERATIONS

Presentation of sample size in this study is based on demonstrating STA® - Liatest® D-Di XL effectiveness in "unlikely" subjects for VTE meets the following performance goals as provided in Table 1A of CLSI guideline (H-59A p. 28):

- Sensitivity

³ U.S. Dept. of HHS, FDA. Guidance for industry: E9 statistical principles in clinical trials. 1998; Section 5.2.1, pp. 28 –

- Lower 95% two-sided confidence interval (LCL) ≥ 0.90
- Point Estimate ≥ 0.95
- NPV
 - LCL 95% two-sided ≥ 0.95
 - Point Estimate ≥ 0.97

While performance goals (PGs) are the same for PE and DVT, power must be calculated separately for each because of different prevalence and accuracy assumptions for PE+ and DVT+. The accuracy assumptions are based on observed results in the studies submitted to FDA⁴. Notwithstanding, blind sample size re-estimation (i.e. counting of positive cases during the trial) will be employed to achieve requisite power. For both PE and DVT sample sizes we assume that at about 70% of reference-positive cases will be from the US and the rest (about 30%) from out of US (OUS).

PE: Power for Meeting PGs

Presentation of sample size is based on obtaining a enough reference-positive cases to achieve 90% power to meet the LCL PG for sensitivity (≥ 0.90), which will necessarily:

- Enable success on the point estimate PG for sensitivity, since the minimum true-positive rate needs to meet the LCL PG, given the sample size reported below, is the same as the minimum needed for the point estimate PG.
- Yield enough reference-negative patients for near 100% power to meet the PGs for NPV, due to low prevalence of positive cases.

Based on the counting of positive cases (allowed by this protocol) to the date of amendment V2.1, we assume:

- US prevalence of reference-positive = 3.4%
- OUS prevalence of reference-positive = 5.7%

Based on historical data, we assume:

- D-Di XL sensitivity = 98%
- D-Di XL NPV = 99.6%

Given the above, N = 115 reference-positive subjects are needed to have at least 90% power to demonstrate efficacy on both sensitivity and NPV⁵. Given at least N = 75 in the US (65%), 2,206 “unlikely” US subjects will be needed (75/0.034). Given N = 40 OUS (35%) at most1, 702 “unlikely” OUS subjects will be needed (40/0.057).

⁴ In these studies, DVT results demonstrate higher accuracy parameters than PE. For the purpose of computing power in this study we assume the PE accuracy observed for both indications.

⁵ Achieving requisite power for sensitivity, rather than NPV, drives the sample size

At the time this protocol amendment is issued, a total of 3,054 PE patients were enrolled including 121 PE positive patients (79 in US and 42 OUS - uncleaned, non-final data), allowing to have 90% power to demonstrate D-Di XL efficacy for PE. The PE data collection has been completed and data cleaning is in progress.

DVT: Power for Meeting PGs

Presentation of sample size is based on obtaining enough reference-positive case to achieve 90% power to meet the confidence interval PG for sensitivity (≥ 0.90), which will necessarily provide:

- The same power to meet the point estimate PG, since the minimum true-positives needed to meet the confidence interval PG is the same as that needed to meet the point estimate PG.
- A sufficient number of reference-negative patients for near 100% power to meet the PGs for NPV, due to low prevalence of positive cases

Based on data previously submitted to FDA, we assume:

- US prevalence of reference-positive = 5.3%
- OUS prevalence of reference-positive = 8.1%
- D-Di XL sensitivity = 98%
- D-Di XL NPV = 99.6%

Given the above, $N = 115$ reference-positive subjects are needed to have 90% power to demonstrate efficacy. Given at least $N = 69$ in the US (60%), at least 1,032 “unlikely” US subjects will be needed ($69/0.053$). Given $N = 46$ OUS (40%) 568 “unlikely” OUS subjects will be needed ($46/0.081$).

In summary, a total of 1,870 subjects are expected to participate in the DVT part of the study—at least 1,032 from the US and at most 568 from OUS—to have 90% power to demonstrate D-Di XL efficacy for DVT.

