- 1) The initial phase (see diagram below) will include sample and data collection from subjects suspected of VTE (PE and/or DVT) at participating sites (“enrolling sites”); subjects will be diagnosed and treated in accordance with routine standard of care (SOC). A test using VIDAS® D-Dimer Exclusion II™ (VIDAS) assay will be conducted on one of the frozen plasma aliquots. The result obtained (i.e. D-Di “reference value”) will be used in the following phase to assess sample stability.

- 2) When the STA® - Liatest® D-Di XL product is ready for clinical testing (see diagram below), frozen samples from unlikely patients will be tested with VIDAS assay and with STA® - Liatest® D-Di XL. The results of the VIDAS assay will be used to assess samples stability. The results from “stable” samples will be used for comparison to reference (imaging or follow-up) and computation of accuracy parameters (sensitivity, NPV, specificity and PPV). STA® - Liatest® D-Di XL and stability testing will be performed at selected sites (“testing sites”). There will be at least 2 testing sites in the US and 2 in Europe.

Procedures for STA - Liatest DDi XL clinical testing

Main inclusion criteria: The study population will be recruited from prospective, consecutive, ambulatory outpatients (presenting at the emergency unit or outpatient clinic) suspected of having VTE. Patients with DVT and PE will be analyzed as separate groups. Therefore, enrolment in each group will be monitored separately and will be stopped when the desired target per indication is reached. Subjects suspected of both DVT and PE will be included in both PE and DVT groups.

Number of Subjects

A sample size of $N = 115$ evaluable reference-positive subjects is needed to achieve at least 90% power to demonstrate sensitivity for PE and DVT separately. This will provide at least 80% power to demonstrate co-primary performance goals for PE and co-primary performance goals for DVT. The samples needed to obtain the number of positives will, due to low prevalence, yield a large number of negative subjects so that power for demonstrating NPV performance goals is about 100% in each indication.

Expected overall study enrolment – PE

Based on actual prevalence data obtained during enrolment, a total of at least 2,908 subjects were expected to participate in the PE study—with at least 2,206 from the US and at least 702 from OUS—to have 90% power to demonstrate STA® - Liatest® DDi XL efficacy for PE.

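### Section 9.5 states a 70/30 US/OUS split of positives that neither sample-size calculation uses, and misprints the DVT US minimum as 1,032 where its own formula gives 1,302

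*Combined protocol and SAP*

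**What the plan says.** The opening part of section 9.5 gives one regional assumption for both sample sizes: "we assume that at about 70% of reference-positive cases will be from the US and the rest (about 30" per cent) from OUS.

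The two calculations that follow each print a different split.

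- **PE:** "Given at least N = 75 in the US (65" per cent) and 40 OUS (35%), giving 2,206 US and 702 OUS subjects. The synopsis gives the total as 2,908. The uncleaned PE positives at Amendment 2.1 are reported as "79 in US and 42 OUS", out of 121.
- **DVT:** 69 positives "in the US (60%), at least 1,032" US subjects, and 46 OUS positives (40%) from 568 OUS subjects. The total is 1,870. The synopsis repeats the 1,032, the 568 and the 1,870.

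Both calculations start from 115 positives. For PE, section 9.5 says that "N = 115 reference-positive subjects are needed to have at least 90% power to demonstrate efficacy on both sensitivity and NPV"; the synopsis says that 115 "evaluable reference-positive subjects is needed to achieve at least 90% power to demonstrate sensitivity for PE and DVT separately".

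**The concern.** Prevalence differs by region (PE 3.4% US and 5.7% OUS; DVT 5.3% and 8.1%). The assumed split of positives therefore determines how many subjects must be enrolled to find 115 of them, and where. A stated assumption that the calculations do not use leaves the reader unsure which split was intended.

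The matter is live for DVT, which was still enrolling when Amendment 2.1 was issued. That amendment is written for US sites, and the US DVT minimum is one of its planning figures. For that one quantity the text supports three values: 1,032 as printed, 1,302 from the printed formula, and about 1,519 from the 70/30 sentence. At stake are the accuracy of the projected DVT enrolment and a clear statement of how much of the DVT sensitivity evidence is expected from the US.

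**Working it through.** **Inputs (section 9.5 and synopsis).** Target of 115 positives per indication; the prevalences above; splits of 75/40 for PE and 69/46 for DVT. No inflation for attrition is stated. Formula: enrolment in a region = positives in that region / prevalence in that region, summed over the two regions.

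**1. Reproduce the plan's totals from the splits printed beside them.**

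| | US | OUS | Total | Plan's total |
|---|---|---|---|---|
| PE, 75/40 | 75/0.034 = 2,206 | 40/0.057 = 702 | 2,908 | 2,908 |
| DVT, 69/46 | 69/0.053 = 1,302 | 46/0.081 = 568 | 1,870 | 1,870 |

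Shares: 75/115 = 65.2% and 69/115 = 60.0%. Observed PE share: 79/121 = 65.3%. Both totals reproduce, and neither comes from 70/30.

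**2. The printed DVT US minimum.** The formula 69/0.053 gives 1,302, not 1,032; the digits look transposed. As printed, 1,032 + 568 = 1,600, which is 270 short of 1,870. Expected positives from the printed parts: 1,032 × 0.053 + 568 × 0.081 = 54.7 + 46.0 = 100.7, about 14 short of 115. The synopsis's overall 4,924 equals 3,054 + 1,870, so it rests on the 1,870 and is not affected by the misprint.

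**3. What 70/30 would have given.** 115 × 0.70 = 80.5 US and 34.5 OUS.

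- PE: 80.5/0.034 + 34.5/0.057 = 2,368 + 605 = 2,973, that is +65 (2.2%) on 2,908.
- DVT: 80.5/0.053 + 34.5/0.081 = 1,519 + 426 = 1,945, that is +75 (4.0%) on 1,870. The US part rises 16.7% on 1,302 and the OUS part falls 25.0% on 568.

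**4. Effect on power.** The rule is "Lower 95% two-sided confidence interval (LCL) ≥ 0.90" by the exact binomial interval, plus a point estimate of at least 0.95. The assumption is "D-Di XL sensitivity = 98" per cent.

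| Evaluable positives | True positives required | Exact power |
|---|---|---|
| 101 | 97 | 94.7% |
| 110 | 106 | 92.9% |
| 111 | 107 | 92.7% |
| 112 | 108 | 92.5% |
| 113 | 109 | 92.3% |
| 115 | 110 | 97.1% |

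Power is not monotone in the count because the number of misses allowed steps from four to five at 114.

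If the stated totals were enrolled and positives did split 70/30, the expected positives would be 1,870/(0.7/0.053 + 0.3/0.081) = 110.6 for DVT and 2,908/(0.7/0.034 + 0.3/0.057) = 112.5 for PE. Power near those counts is about 92% to 93%, above the stated 90%.

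**The case against.** The strongest reply is that one sentence is out of line and nothing depends on it. Each calculation prints its own split and division, so the operative assumption is disclosed. Section 9.2 ends the trial on positives recruited, not on subjects enrolled, and the synopsis and section 9.5 provide for blinded re-estimation by counting positives. PE has 3,054 enrolled and 121 uncleaned positives, which exceeds the total under either split. All of this stands, and it limits the point to the accuracy of the stated figures.

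A reader might infer from the 70/30 sentence that the totals 2,908 and 1,870 are too low. The documents do not support that. It would require the unused sentence to override the splits printed in the calculations, and the one observed split, PE at 65/35, agrees with the calculation. No DVT positives by region are reported, so neither 60/40 nor 70/30 can be checked for DVT. A reader might also infer a shortfall in US sensitivity evidence. No success criterion in section 9.6 is region-specific; region enters only as a poolability covariate.

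Could 70/30 describe enrolled subjects? That fits DVT (1,302/1,870 = 69.6%) but not PE (2,206/2,908 = 75.9%), and the sentence refers to reference-positive cases.

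Finally, 1,032 is worded as a minimum, so a larger US number would not breach it. But with OUS capped at 568 and a total of 1,870, the US number must be at least 1,302. The printed bound therefore disagrees with the total as well as with its formula.

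**Conclusion.** The point holds as two errors in stated planning figures. First, the 70/30 sentence contradicts both calculations (65/35 and 60/40), and no text explains the change. Second, the DVT US minimum of 1,032 is wrong by the plan's own formula, by 270 subjects; this is the larger error and would remain if the 70/30 sentence were deleted.

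It is not a loss of power. The target of 115 does not depend on the split, and blinded counting protects it. Even at the counts expected from the stated totals under 70/30, or from the misprinted DVT parts, exact power stays above 90%. Those power figures assume 98% sensitivity and treat expected positives as evaluable. The correction is worth making because DVT was still enrolling when the amendment was issued; for PE it is a matter of record only.

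**What to change.** In section 9.5, replace the 70/30 sentence with the splits actually used: about 65/35 for PE, noting the observed 79/42, and 60/40 for DVT with the basis for it. Correct the DVT US minimum from 1,032 to 1,302 wherever it appears in section 9.5 and in the synopsis, so that 1,302 + 568 = 1,870.

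Check the 60/40 split against the blinded DVT counts of positives by region. Only if these show a split nearer 70/30 should the DVT projection be restated, at about 1,519 US + 426 OUS = 1,945, with the study total updated to match.

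The cost is wording and one figure. The target of 115, the hypotheses and the analysis are unchanged, and the totals 1,870 and 4,924 stay as they are unless the DVT split is revised.
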